6.4.5. Visit 11 (Week 28)

For subjects who agree to continue with additional visits (Visit 12-15) at Visit 10, Visit 11 should be marked as not done, unless Visit 11 is when the subject consents to the additional Visits 12-15.

This visit must occur 28 weeks (± 14 days) after Visit 2.

At this visit, the investigator or designee will perform the following procedures:

1. Query the subject in a non-directive manner about any changes in her/his health since the previous visit and report all AEs on the appropriate form
2. Query the subject about any changes in her/his concomitant therapies since the previous visit and report changes on the appropriate form
3. Confirm the subject continues to comply with all study requirements and has followed all study instructions
4. Conduct a physical examination
5. Measure vital signs
6. Conduct an ECG
7. Collect blood samples for clinical laboratory tests
8. Perform a urine pregnancy test for WOCBP
9. Have the subject perform an LTA
10. The investigator or designee will perform an LTA
11. The investigator or designee will perform the F-VASI
12. Have the subject complete the VNS
13. Have the subject complete the SVSS
14. Have the subject complete the VitiQoL
15. Take standardized photographs

16. Discharge the subject from the study, unless the subject agrees to continue with additional study visits (Visit12-15).
17. For subjects who agree to continue with additional study visits (Visits 12-15).
 - a. Obtain consent for additional study visits, Visit 12-15.
 - b. Dispense study medication.
 - c. Review study instructions with the subject.
18. Schedule Visit 12, 32 weeks from Visit 2.

6.4.6. Visit 12 (Week 32)

This visit must occur 32 weeks (\pm 7 days) of Visit 2.

At this visit, the investigator or designee will perform the following procedures:

1. Query the subject in a non-directive manner about any changes in her/his health since the previous visit and report all AEs on the appropriate form.
2. Query the subject about any changes in her/his concomitant therapies since the previous visit and report changes on the appropriate form.
3. Confirm the subject continues to comply with all study restrictions and has followed all study instructions.
4. Measure vital signs.
5. Collect blood samples for clinical laboratory tests.
6. Perform a urine pregnancy test for WOCBP.
7. Perform the F-VASI.
8. Have the subject complete the VNS.
9. Have the subject complete the SVSS.
10. Dispense and collect study medication.
11. Take standardized photographs.
12. Review the study instructions with the subject.
13. Schedule the Visit 13 40 weeks \pm 7 days from Visit 2.

6.4.7. Visit 13 (Week 40)

This visit must occur 40 weeks (\pm 7 days) of Visit 2.

At this visit, the investigator or designee will perform the following procedures:

1. Query the subject in a non-directive manner about any changes in her/his health since the previous visit and report all AEs on the appropriate form.
2. Query the subject about any changes in her/his concomitant therapies since the previous visit and report changes on the appropriate form.
3. Confirm the subject continues to comply with all study restrictions and has followed all study instructions.
4. Measure vital signs.
5. Collect blood samples for clinical laboratory tests.
6. Perform a urine pregnancy test for WOCBP.
7. Perform the F-VASI.
8. Have the subject complete the VNS.
9. Have the subject complete the SVSS.

10. Dispense and collect study medication.
11. Take standardized photographs.
12. Review the study instructions with the subject.
13. Schedule the Visit 14 48 weeks \pm 7 days from Visit 2.

6.4.8. Visit 14 (Week 48)

This visit must occur 48 weeks (\pm 7 days) of Visit 2.

At this visit, the investigator or designee will perform the following procedures:

1. Query the subject in a non-directive manner about any changes in her/his health since the previous visit and report all AEs on the appropriate form.
2. Query the subject about any changes in her/his concomitant therapies since the previous visit and report changes on the appropriate form.
3. Confirm the subject continues to comply with all study restrictions and has followed all study instructions.
4. Measure vital signs.
5. Collect blood samples for clinical laboratory tests.
6. Perform a urine pregnancy test for WOCBP.
7. Perform the F-VASI.
8. Have the subject complete the VNS.
9. Have the subject complete the SVSS.
10. Collect study medication.
11. Have the subject complete the VitiQoL.
12. Take standardized photographs.
13. Review the study instructions with the subject.
14. Schedule the Visit 15 52 weeks \pm 7 days from Visit 14.

6.4.9. Visit 15 (Week 52)

This visit must occur 52 weeks (\pm 7 days) of Visit 2.

At this visit, the investigator or designee will perform the following procedures:

1. Query the subject in a non-directive manner about any changes in her/his health since the previous visit and report all AEs on the appropriate form.
2. Query the subject about any changes in her/his concomitant therapies since the previous visit and report changes on the appropriate form.
3. Confirm the subject continues to comply with all study restrictions and has followed all study instructions.
4. Measure vital signs.
5. Conduct an ECG.
6. Perform a physical examination.
7. Collect blood samples for clinical laboratory tests.
8. Perform a urine pregnancy test for WOCBP.
9. Perform the F-VASI.

10. Perform the total body VASI.
11. Have the subject complete the VNS.
12. Take standardized photographs.
13. Discharge the subject from the study.

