Mean change from baseline in total VASI from baseline (Visit 2) to Week 4, 8, 12, 16, 20 24 and 48 (Visits 5-15) will be assessed for descriptive purposes only to track disease progression in untreated areas.

Safety analyses will include descriptive statistics calculated on the safety parameters using the safety population. The proportion of subjects with treatment-emergent adverse events will be tabulated and presented by treatment and Medical Dictionary for Regulatory Activities (MedDRA) System Organ Class. Vital signs and clinically relevant abnormal laboratory results will also be tabulated and presented. Change from baseline (Visit 2) in the Local Tolerability Assessments (LTA) to end of treatment (Visit 10) will be summarized.

Data from all enrolled and treated subjects will be presented and summarized. Safety summaries will include listings by study medication of adverse events incidences within each MedDRA System Organ Class, and changes from pre-application values in vital signs. Adverse event summaries will be presented showing the proportion of subjects experiencing adverse events, both overall and by MedDRA System Organ Class.

TABLE OF CONTENTS

1. SYNOPSIS	6
2. INTRODUCTION.....	18
2.1. Summary.....	18
3. STUDY RATIONALE.....	20
3.1. Study Rationale.....	20
4. STUDY OBJECTIVES	20
4.1. Primary Objective	20
4.2. Secondary Objectives	20
5. SELECTION AND DISPOSITION OF STUDY POPULATION	20
5.1. Number of Subjects and Study Sites	20
5.2. Study Population Characteristics.....	20
5.3. Inclusion Criteria.....	21
5.4. Exclusion Criteria.....	21
5.5. Previous and Concomitant Medications and Therapies.....	23
5.6. Permitted Concomitant Medications, Therapies and Over the Counter Products (OTC)	23
5.6.1. Prohibited and/ or Restricted Medications	24
5.7. Subject Identifier (SI)	24
5.8. Replacement Subjects	25
5.9. Subject Withdrawal Criteria	25
5.10. Study Termination	25
6. INVESTIGATIONAL PLAN.....	26
6.1. Overall Study Design.....	26
6.2. STUDY PROCEDURES	26
6.3. Schedule of Assessments	27
6.4. Study Visits Description and Procedures	30
6.4.1. Visit 1/ Screening (Day -28 to 0)	30
6.4.2. Visit 2 (Day 1) / Baseline.....	30
6.4.3. Visit 3-9 (Weeks 1, 2, 4, 8, 12, 16 and 20) These visits must occur on the following weeks after Visit 2:	32
6.4.4. Visit 10 (Week 24).....	32
6.4.5. Visit 11 (Week 28).....	33
6.4.6. Visit 12 (Week 32).....	34

6.4.7. Visit 13 (Week 40).....	34
6.4.8. Visit 14 (Week 48).....	35
6.4.9. Visit 15 (Week 52).....	35

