8.1.4. Vitiligo Area Scoring Index (VASI)

The VASI will be assessed by the investigator or designee to track the total body vitiligo status throughout the study at screening (Visit 1), baseline (Visit 2), Week 12 (Visit 7), Week 24 (Visit 10), and Week 48 (Visit 14). The body is divided into the following 6 separate and mutually exclusive sites: head/neck, hands, upper extremities (excluding hands), trunk, lower extremities (excluding feet), and feet. The investigator or designee will assess each of the 6 body sites using a Wood's lamp to assist in the identification of the vitiliginous lesions.

The percentage of vitiligo involvement for each body region is calculated using the palmar method. The palmar method uses the palmar surface area of the investigator or designee's hand as an estimation guide and defines the surface of the evaluator's hand including fingers to be 1.0% of the total body surface area. Each of the 6 body sites is then clinically evaluated by visual assessment for the pattern of skin depigmentation using a visual scale. The publication by Hamzavi I, Jain H, McLean D, Shapiro J, Zeng H, and Lui H. 2004 will be provided to the investigators to depict the pattern of depigmentation as illustrated in descriptive patient photographs.

Total body VASI = Sum of all the values from the body sites (in Hand units) x (Residual depigmentation)

- **Hand unit** - One hand unit is approximately 1% BSA – used as a guide to estimate % of vitiligo involvement in each body area. (Body is divided into 6 areas)
- **Extent of residual depigmentation** is expressed by the following percentages:
 - 0
 - 10% - only specks of depigmentation are present
 - 25% - the pigmented area exceeds the depigmented area
 - 50% - the depigmented and pigmented areas are equal
 - 75% - the depigmented area exceeds the pigmented area
 - 90% - specks of pigment are present
 - 100% - no pigment is present

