11.2. Statistical Methods

Summary descriptive statistics (N, mean, median, SD) by visit will be provided for all safety and efficacy parameters. Primary and secondary efficacy parameters are described below:

Primary Efficacy Parameter

Mean change from baseline in facial depigmentation in the AOI will be quantified using Canfield-2-D photographic image analysis from baseline (Visit 2) compared to Week 48 (Visit 14).

Secondary Efficacy Parameters:

Mean change from baseline in facial depigmentation will be calculated as the mean change in Facial assessment of the Vitiligo Area Scoring Index (F-VASI) from Visit 2 compared to Week 24 (Visit 10) and if applicable, Week 48 (Visit 14). F-VASI is a modification of the validated quantitative assessment scale for vitiligo which evaluates the percentage of vitiligo involvement of the face only.

Mean change from baseline in facial depigmentation in the AOI based on Canfield 2-D Photographic analysis from Visit 2 compared to Weeks 4, 8, 12, 16, 20, 24, 32, 40, and post-treatment Week 52 (Visits 5-11, and 12, 13, and 15).

Mean change from baseline in the Facial assessment of the Vitiligo Area Scoring Index (F-VASI) from Visit 2 compared to Weeks 4, 8, 12, 16, 20, 24, 32, 40, 48 and post-treatment Week 52 (Visits 5-11, and Visits 12, 13, 14 and 15).

Mean change from baseline in the VitiQoL from Visit 2 compared to Week 12, 16, 20, 24, and 48 (Visits 7-10, 14).

Treatment success based on the subject's assessment of vitiligo on the Vitiligo Noticeability Scale (VNS) at Week 4, 8, 12, 16, 20, 24, 32, 40, and 48.

Mean change from baseline in total VASI from Visit 2 to Visits 7 and Visit 14 (Week 48) will be assessed for descriptive purposes only to track disease progression in untreated areas.

Safety analyses will include descriptive statistics calculated on the safety parameters using the safety population. The proportion of subjects with treatment-emergent adverse events will be tabulated and presented by Medical Dictionary for Regulatory Activities (MedDRA) System Organ Class. Vital signs and clinically relevant abnormal laboratory results will also be tabulated and presented. Change from baseline in the Local Tolerability Assessments (LTA) to end of treatment (Visit 10) will be summarized.

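### Total body VASI is missing from the Visit 14 procedure list and appears at Visit 15 instead, against the schedule, 8.1.4 and 11.2; its total also mixes treated with untreated skin

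*Combined protocol and SAP*

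**What the plan says.** **Collection.** The Visit 14 list in 6.4.8 has 14 items, and its only VASI item is "Perform the F-VASI". Item 10 of the Visit 15 list in 6.4.9 is "Perform the total body VASI". Section 8.1.4 sets the post-baseline assessments at "Week 12 (Visit 7), Week 24 (Visit 10), and Week 48 (Visit 14", with no mention of Visit 15. The schedule for Visits 12 to 15 in 6.3 has one mark for total body VASI, at Visit 14.

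**Analysis.** Section 11.2 specifies "Mean change from baseline in total VASI from Visit 2 to Visits 7 and Visit 14 (Week 48". The Statistical Methods part of the synopsis gives a longer list, "to Week 4, 8, 12, 16, 20 24 and 48 (Visits 5-15".

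**Purpose and construction.** Section 11.2 says that the measure "will be assessed for descriptive purposes only to track disease progression in untreated areas". Section 8.1.4 defines the total as "Sum of all the values from the body sites (in Hand units" multiplied by residual depigmentation, over six sites, one of which is head/neck. Under 7.3, study drug is applied to the face and neck.

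**The concern.** Two things look wrong.

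First, the visit lists that sites are likely to use as a checklist move the assessment from the last on-treatment visit to the follow-up visit. A Week 48 body assessment that was not done cannot be recovered later. If some sites follow the lists and others the schedule, the Week 48 summary would have gaps that run by site, in a study of only 33 subjects.

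Second, the total is not a clean measure of what it is meant to track. If the face repigments under study drug, the total falls even when nothing changes elsewhere. It could also stay flat while other sites worsen.

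**Working it through.** The documents give no figure to reproduce for this point. The check sets the sections side by side, works out the visit windows, and writes out the composition of the score.

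**1. Post-baseline visits for total body VASI, by source**

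| Source | Visits named |
|---|---|
| 6.4.3 (Visits 3 to 9) | Visit 7 only |
| 6.4.4 (Visit 10) | Visit 10 |
| 6.4.5 to 6.4.7 (Visits 11, 12, 13) | none |
| 6.4.8 (Visit 14) | none |
| 6.4.9 (Visit 15) | Visit 15 |
| 6.3, extension schedule | Visit 14 |
| 8.1.4 | Visits 7, 10, 14 |
| 11.2, total-VASI sentence | Visits 7, 14 |
| Synopsis, Statistical Methods | Weeks 4, 8, 12, 16, 20, 24, 48; bracket gives Visits 5 to 15 |

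The single extension mark sits in the same column as VitiQoL, which 6.4.8 and 8.1.6 both place at Visit 14. I do not rely on the Visit 1 to 11 schedule row, because its column alignment is uncertain in the extracted text.

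Three conflicts follow:
- 6.4.8 and 6.4.9 disagree with 6.3, 8.1.4 and 11.2 on Visit 14 against Visit 15.
- The 11.2 sentence leaves out Visit 10, where 6.4.4 and 8.1.4 collect the measure.
- The synopsis names Weeks 4, 8, 16 and 20, when it is not collected. Its bracket also runs to Visit 15 (Week 52), while its list of weeks stops at 48.

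**2. Can a Visit 15 value stand in for Week 48?** Inputs are from the extension schedule.
- Visit 14: Day 337 ± 7 = Days 330 to 344.
- Visit 15: Day 365 ± 7 = Days 358 to 372.
- Smallest gap: 358 − 344 = 14 days.

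The windows do not overlap, Visit 15 is a post-treatment visit, and no rule maps its data to Week 48. It cannot stand in.

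**3. Early withdrawal.** Section 5.9 sends subjects who leave during the extension to the Visit 15 assessments. Under 6.4.9 those subjects have a total body VASI; under the schedule they do not.

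**4. Effect of including head/neck.** Let H be the baseline head/neck VASI, B the baseline sum of the other five sites, and r the fractional fall in H, with B unchanged. Then

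relative change in total = −rH / (H + B) = −r × s, where s = H / (H + B).

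The documents give neither r nor s. The figures below use assumed values and only show how the result depends on s. Take r = 0.5 and B = 3.0, 1.5 or 0.75.
- H = 0.75: 0.375/3.75 = 10.0%; 0.375/2.25 = 16.7%; 0.375/1.5 = 25.0%.
- H = 0.25 (the 0.25% facial entry minimum, taken as fully depigmented and as the only head/neck involvement): 0.125/3.25 = 3.8%; 0.125/1.75 = 7.1%; 0.125/1.0 = 12.5%.

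Masking is possible too. With H = 0.75 falling to 0.375 and B = 1.5 rising by 25% to 1.875, the total is 2.25 both before and after.

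**The case against.** The strongest reply is that the protocol already says which text governs. Section 6.2 has staff perform assessments according to the schedule in 6.3, which marks Visit 14, and 8.1.4 repeats it. A site following 6.2 collects the Week 48 value. This stands, and it makes the loss conditional. It does not remove the conflict, because each 6.4 list also states directly what the investigator or designee will do at that visit.

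A reader might infer that all Week 48 values will be lost. The documents do not support that: nothing in them suggests that sites use 6.4 in preference to 6.3.

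A reader might also infer that leaving Visit 10 out of the 11.2 sentence loses the last reading for subjects who do not continue. That does not follow. The Visit 10 value is collected, the synopsis names Week 24, and the opening of 11.2 promises by-visit summaries for all efficacy parameters, which arguably covers it. What remains is an incomplete sentence.

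On head/neck, it is fair to say that any percentage is assumed, that the six sites are scored separately so another sum can be derived at any time, and that head/neck contains some untreated skin, such as the eyelids. All of this stands. It limits the size of the point but does not resolve the mismatch between the stated purpose and the score that is summarised.

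**Conclusion.** The inconsistency is real and can be read directly in the plain text of 6.4.8, 6.4.9, 8.1.4 and 11.2. Its consequence is a risk of missing or uneven Week 48 total VASI data, confined to sites that work from the 6.4 lists. The documents do not allow the number of affected subjects to be estimated.

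The stakes are modest. Total VASI is descriptive only, with no test or decision attached. The photographs for the primary endpoint and the F-VASI are both in the Visit 14 list, so neither is affected.

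The head/neck point holds in direction: with the other sites unchanged, a facial response lowers the total by r × s. Its size cannot be stated, because s varies by subject and is not given. The worked percentages are illustrations and should not be quoted as an expected effect.

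This should be corrected, but it does not threaten the study's main results.

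**What to change.** 1. Add total body VASI to 6.4.8. Then either remove it from 6.4.9, or keep it there and state that Visit 15 is an additional off-treatment reading, including for early withdrawals sent to Visit 15 assessments under 5.9. Align the schedule, 8.1.4, the synopsis and 11.2 with that choice.
2. Name Visit 10 in the total-VASI sentence of 11.2.
3. For the untreated-areas purpose, summarise the sum of the five sites other than head/neck alongside the six-site total.

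The cost is protocol wording and one derived variable. No new data are needed, since Visit 14 only gains an assessment that the schedule already requires. One small downside is that the five-site sum leaves out the untreated part of head/neck, which is why it should sit beside the total and not replace it.

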7. STUDY TREATMENT

7.1. Investigational Study Medication

The study medication for this study is ATI-50002 Topical Solution, 0.46%. The study medication is a thin clear solution. The inactive ingredients include: water, Transcutol P, propylene glycol, PEG400, dimethyl sulfoxide (DMSO), Kolliphor CS 20, benzyl alcohol, poloxamer 188, and povidone K30.

STUDY MEDICATION INFORMATION	
Study medication name	ATI-50002
Dosage Strength	0.46%
Manufacturer	PMRS, Inc., Horsham, PA
Pharmaceutical Form	Topical Solution
Container	Amber Glass Bottle, 30 mL with screw cap (20mL fill) Amber Glass Bottle, 120 mL with screw cap (100mL fill)
Storage Conditions	59°F to 77°F (15°C to 25°C)
Dose regimen	
Route	Topical
Frequency	Twice-daily
Duration of administration	Up to 48 weeks
Other supplies	Disposable, single-use applicators will be provided.

7.2. Subject Study Medication Assignment

At Baseline (Visit 2), an investigational center staff member will assign study medication to eligible subjects by selecting an appropriate Subject Kit. The staff member must select Subject Kits in chronological sequence and in an ascending numerical order starting with the lowest available Subject Kit number. No Subject Kit number may be omitted or reused.

The investigational staff member will enter the subject identifier, subject initials, and date dispensed on the Subject Kit label, and record the Subject Kit number in the subject's eCRF.

The site will dispense study medication bottles provided in the individual Subject Kits first and then dispense the individual 120 ml (100 ml fill) bottles to the subject, as needed.

7.3. Application of Study Medication

Subjects will be instructed to apply a thin film of ATI-50002 Topical Solution, up to 2-mL, twice-daily; once in the morning and approximately 8-12 hours later to the vitiliginous areas of the face and neck including a $\frac{1}{2}$ " inch margin around these areas (excluding: the area from the bony rim of the orbit to and including the upper and lower eyelids; and mucosal lip areas) following the instructions in APPENDIX 1. The subject must wash her/his hands thoroughly before and after each study drug application. At each study visit, subjects should bring the study medication including unused bottles. The disposable applicators should be disposed of at the subject's home out of the reach of children.

Following review of study medication instructions, subjects will apply the first dose of study medication in the office under the instruction and supervision of the study staff.

During the Baseline visit (Visit 2), the study staff member will:

- Dispense the appropriate study medication bottle.
- Weigh the bottle with the cap prior to the first study medication application.
- Instruct the subject on the appropriate application technique following instructions in APPENDIX 1.
- Observe the subject's first study medication application to ensure proper coverage and monitor the subject for at least 20 minutes.
- After the first application, the study staff should weigh the study bottle with the cap.
- Dispense the study medication to the subject.
- Provide feedback on the application procedure, if needed.

If the subject develops a new patch of vitiligo on the face or neck during the study, the investigator or designee will instruct the subject to treat the new area of facial vitiligo. The investigator must incorporate the new area of facial vitiligo, once it is clinically evident, into the F-VASI assessment. New areas of vitiligo on the face or other body areas that develop during the study are not considered adverse events.

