5.3. Inclusion Criteria

In order to be eligible for the study, a subject must fulfill all of the following criteria:

1. Subject is a male or female \geq 18 years of age.
2. Subject has a clinical diagnosis of new onset or actively progressing non-segmental facial vitiligo or worsening of existing facial lesions within the past 6 months. Actively progressing vitiligo is defined as: subject history of a new vitiliginous lesion or objective signs of disease activity (such as: confetti-like depigmentation, trichrome lesions, and the Koebner phenomenon) as assessed by the investigator. Subjects may have non-facial vitiliginous lesions that are unchanged for more than 6 months provided they meet the requirement for active facial lesions.
3. Subject has non-segmental facial vitiligo effecting at least 0.25% total body surface area (TBSA) (excluding: the area from the eyebrows to and including the upper eyelids, the area from the bony rim of the orbit to and including the lower eyelids; mucosal lip areas; beard [if applicable]; and forehead and chin areas covered by the stereotactic positioning device for photography) with at least one area of the face with normal pigmentation. The face is defined as the area from the border of the hairline, not including hair bearing skin (eyebrows and beard, if applicable) to the jawline.
4. Women of childbearing potential (WOCBP) must have a negative serum pregnancy test at the screening visit and a negative urine pregnancy test at the baseline visit and must agree to use an approved method of highly effective birth control for the duration of the study and for 30 days after last study medication application.
5. If female, subject who is non-pregnant and non-lactating and not planning a pregnancy during the duration of the study.
6. Subject is in good general health and free of any known disease state or physical condition which, in the opinion of the investigator, would interfere with the study assessments or put the subject at undue risk by study participation.
7. Subject is willing and able to follow all study instructions and to attend all study visits.
8. Subject agrees to refrain from any other treatments for vitiligo from the screening visit through the final follow-up visit. Over the counter (OTC) preparations deemed acceptable by the investigator and camouflage makeups are permitted.
9. Subject is able to comprehend and willing to sign an Informed Consent Form (ICF).

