8.1. Assessments of Efficacy

8.1.1. Canfield 2D Digital Facial Image Analysis

A qualified investigational staff member will take 18 photographs (5 lighting modalities x 3 views [left, front, right]) of the face at baseline and then monthly during the study. Each imaging session includes a sequence of images including the following lighting/capture modalities:

- Standard 1 (default settings) – General purpose white light photograph, the typical “clinical” photo. Provides balanced cross lighting for good subjective evaluation of most skin features.
- Standard 2 (default settings) – ‘Diffuse light’. Provides even, white light across the entire image with a minimum of highlight and shadow. Ideal for many quantitative image analysis applications.
- Cross Polarized (default settings) – Polarized light sources with a Perpendicular polarizer over the camera lens. Filters out surface reflections for superior visualization of sub-surface detail (vascular features, erythema, pigment, etc.)

- UV Fluorescence - NF (default settings) – UV filters (365nm band pass) over powerful strobes captured through an un-attenuated lens. The Fluorescence photo is geared toward enhancing the visibility of pigment features that absorb UV light. Fluorescing Porphyrin details are also visible.
- Parallel Polarized (default settings) – Polarized light sources with a Parallel polarizer over the camera lens. Passes only surface reflections for superior visualization of topographical data (wrinkles, fine lines, pores, etc.)

Equipment, supplies, training and detailed instructions for obtaining and managing photographs will be provided to the investigational center prior to the initiation of subject enrollment.

Canfield Scientific will conduct image analysis. The obtained cross-polarized image will be transformed using Canfield's RBX technique to separate melanin (Brown image) from hemoglobin (Red image). A segmentation algorithm detects hyperpigmentation (pigmented areas with concentration higher than normal skin concentration) and depigmentation (pigmented areas with concentration lower than normal skin concentration) within the areas of interest (AOI) from the RBX Brown images. Area of detected pigmentation and intensity measurements can be reported by the algorithm after segmentation. The measurement will be the ratio of the detected area of pigmentation and the AOI. The primary endpoint will be based on the quantification of depigmentation in the AOI over time.

Area of Interest

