9.1. Definitions

9.1.1. Adverse events (AE)

An AE is any untoward medical occurrence in a subject administered a study medication(s) and which does not necessarily have a causal relationship with the study medication. An AE can therefore be any unfavorable and unintended sign or symptom associated with the use of a study medication (including an abnormal laboratory finding), whether or not related to the study medication.

Thus, any new, clinically significant worsening of an existing sign, symptom or disease, should be considered an AE.

Every new episode or clinically significant worsening of a chronic condition (e.g., headaches, seasonal allergies, depression, or hypertension) should be reported as a separate AE, even if the condition is reported in the subject's medical history.

The investigator should, when certain, report a diagnosis rather than the signs, symptoms or clinically significant abnormal laboratory values associated with the AE. Otherwise, signs, symptoms or abnormal laboratory values may be used to describe the AE.

Any CS abnormality discovered prior to the first study medication treatment should be reported as medical history, not as an AE.

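### New vitiligo patches are exempt from AE reporting (7.3), clinically significant growth of existing lesions is not (9.1.1), and new patches in treated skin suspected to be drug-related have no stated exception

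*Combined protocol and SAP*

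**What the plan says.** Section 7.3 deals with a patch that appears on the face or neck during the study. The subject is told to treat it, and for the face the section adds: "The investigator must incorporate the new area of facial vitiligo, once it is clinically evident, into the F-VASI assessment". The next sentence sets its AE status: "New areas of vitiligo on the face or other body areas that develop during the study are not considered adverse events". That sentence covers the whole body. It has no exception for treated skin, suspected relatedness or seriousness, and 7.3 says nothing about existing lesions that enlarge.

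Section 9.1.1 gives the general rule: "Thus, any new, clinically significant worsening of an existing sign, symptom or disease, should be considered an AE". It also treats "Every new episode or clinically significant worsening of a chronic condition" as a separate AE, even when the condition is in the medical history. It neither exempts vitiligo nor refers to 7.3.

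Section 11.2 builds the safety summary on these definitions: "The proportion of subjects with treatment-emergent adverse events will be tabulated", by MedDRA System Organ Class. Section 4.1 places safety and tolerability in the primary objective beside efficacy. Inclusion criterion 2 (section 5.3) admits only subjects whose facial disease is newly arisen, progressing or worsening.

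**The concern.** Vitiligo can progress by growth of an old lesion or by a new patch. For a safety summary these are the same kind of event, but the two sections treat them differently. The exemption also sits in the dosing section rather than in section 9, so a site that works from section 9 could report a patch that another site leaves out.

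The second issue is local. Subjects apply the solution to a half-inch margin around each lesion as well as to the lesion, so new depigmentation can arise in skin that was pigmented when treatment of it began. If it is called vitiligo, it leaves the AE system whatever the investigator suspects. At stake are a consistent reading of the TEAE proportion and the record of a local change opposite to the intended effect.

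**Working it through.** No calculation in the plan bears on this point. Section 11.1 states that no formal power calculation was done, and no AE or progression rate is given. The check is a comparison of the sections.

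**1. Events against the two rules**

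| Event | Section 7.3 | Section 9.1.1 | In the TEAE count? |
|---|---|---|---|
| Clinically significant growth of an existing lesion | Silent | AE | Yes |
| New patch, labelled vitiligo | Not an AE | Can be read as worsening or a new episode | No if 7.3 governs; yes if a site follows 9.1.1 |
| New patch in treated skin, labelled vitiligo, drug suspected | Not an AE, no exception | As above | As above |
| Depigmentation judged a drug reaction, not vitiligo | Not covered | AE | Yes |
| Application-site irritation | Not covered | AE | Yes |

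**2. Either reading leaves a gap.** If 7.3 is a specific exception, rows 1 and 2 are classified differently although the progression may be equal. If 9.1.1 is applied alone, row 2 is reportable and conflicts with 7.3. Row 3 has no provision of its own under either reading.

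**3. What an exempted patch loses.** The relatedness judgement in 9.1.6 is made for AEs. The follow-up beyond the last visit in 9.2.1 is for AEs rated related. An exempted patch gets neither.

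**4. What other measures record.**
- *Canfield analysis* (8.1.1): "The primary endpoint will be based on the quantification of depigmentation in the AOI over time". It and the F-VASI give net facial values, so repigmentation in one place can offset a new patch in another.
- *Treated skin outside both measures.* The face and the AOI end at the jawline, so the neck is outside. Appendix 6 also allows treatment of areas behind the positioning device, the eyebrow area and the beard, which are outside the AOI or the F-VASI.
- *Total body VASI* has a head/neck site. Section 8.1.4 schedules it after baseline at Visits 7, 10 and 14 (6.4.9 also lists it at Visit 15). Section 11.2 says that it "will be assessed for descriptive purposes only to track disease progression in untreated areas".
- *LTA* (8.2.5) grades erythema, edema and scaling/dryness, plus subject-reported symptoms, at Visits 2-11. It has no depigmentation item.
- *Section 11.2* has no count of subjects with new patches.

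**5. Size.** With 33 subjects treated, each subject who has no other TEAE and is counted or not counted moves the overall TEAE proportion by 1/33 = 0.030, or 3.0 percentage points. How many subjects that would be cannot be derived from the documents.

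**The case against.** The best defence is that progression of the disease under study is recorded as efficacy, which is a legitimate choice. New facial patches go into the F-VASI, AOI depigmentation is the primary endpoint, the VNS has a grade for more noticeable vitiligo, and total body VASI follows the rest. On this view 7.3 is a specific exception to a general rule, and a 33-subject open-label pilot with descriptive statistics loses little.

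Much of this stands. Facial worsening is not lost from the trial, and 7.3 is better described as an incomplete exemption than as a flat contradiction. With no control group described, AE reporting could not separate a drug effect from natural course. It would still preserve the investigator's judgement on timing and location, which 9.1.6 asks for. The defence does not explain why growth and new patches are classified differently, and it does not cover the treated neck well.

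A reader might go further and infer that the plan cannot record drug-induced depigmentation in treated skin. The documents do not support that. Section 7.3 names only new areas of vitiligo, so depigmentation judged a drug reaction is not literally excluded. Worsening of an existing treated lesion stays reportable under 9.1.1. Irritation from the solution is reportable too: section 6.1 includes local site reactions among AEs and 7.6 deals with application-site AEs. The criterion 2 wording, "objective signs of disease activity (such as: confetti-like depigmentation, trichrome lesions, and the Koebner phenomenon", lists signs of activity for eligibility; nothing says that the solution induces the Koebner phenomenon.

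A reader might also see a conflict between 7.3 and 9.1.6. There is none: 9.1.6 applies to events that are already AEs and does not define what an AE is.

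**Conclusion.** The point holds as an incomplete exemption without a cross-reference. Whether progression enters the TEAE proportion depends on whether it appears as growth or as a new patch. A new patch labelled vitiligo in treated skin, including the half-inch margin and the neck, gets no relatedness rating or related-AE follow-up.

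The size is unknown. It is tempting to assume progression rates and derive a range of percentage points, but the documents give no such rates. Section 9.1.1 also requires clinical significance, so not every enlargement would count. The primary endpoint is unaffected.

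The conclusion assumes that sites apply the text as written and that some subjects progress on treatment, which is plausible given criterion 2.

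**What to change.** Put one rule in 7.3 and 9.1.1, each referring to the other. It should classify new and enlarging vitiligo lesions the same way. It should also state that new or enlarging depigmentation in treated skin which the investigator suspects is related to study medication, or which is serious, is reported as an AE. Since 9.1.1 defines an AE regardless of causality, any exemption for other progression should be written there as an explicit exception.

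Add one eCRF item for a new face or neck patch, which 7.3 already expects the investigator or designee to identify and have treated. Complete it after the F-VASI is scored, because 8.1.2 bars reference to other visits while scoring. In 11.2, list the number of subjects with such patches beside the TEAE table.

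A table of enlarging lesions split by treated and untreated skin should not be added. The F-VASI is a single net score rated without reference to other visits, and untreated skin is scored at only a few visits, so the data would not support the split.

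The cost is protocol wording, one extra eCRF line and a few more AE entries that need a relatedness judgement.
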